9.4.5 Selection and Timing of Dose for Each Subject

E2609 is administered orally, QD, with food. Study treatment will begin on Day 1 following randomization and will continue for approximately 78 weeks.

9.4.6 Blinding

E2609 and placebo will be administered as tablets of identical appearance.

During the Randomization Phase and Follow-Up Phases, subjects, caregivers/informants, and all clinical site personnel involved with the conduct and interpretation of the study, including investigators will be blinded to the treatment codes (double-blind). In order to make decisions about the remainder of the study as well as the full E2609 clinical development program, the sponsor will unblind safety, PK, and PD data on an ongoing basis and perform interim analyses of these data. (revised per Amendment 03)

Every effort should be made to keep the site staff responsible for reviewing laboratory reports and assessing AEs separate from the site staff responsible for the efficacy assessments, particularly for the CDR (ie, those who are trained and certified to perform the various cognitive assessments that are undertaken in this study). Furthermore, at the site, the notes and reports relating to safety assessments must be kept separate from the notes and reports relating to efficacy, particularly for the CDR. (revised per Amendment 01)

Randomization data will be kept strictly confidential, filed securely by an appropriate group with the sponsor or CRO and accessible only to authorized persons (eg, Eisai Global Safety) until the time of unblinding, per the standard operating procedure.

The PK/PD interim analyses will take place throughout the study as per Amendment 03 and will be conducted by an independent PK/PD scientist at the sponsor. Any additional changes to dose required for this study will be reflected in a further amendment to the protocol and the Statistical Analysis Plan will detail how data will be handled in the primary analysis. (revised per Amendments 02 and 04)

In the event that emergency conditions require knowledge of the study treatment given, the blind may be broken via the code breaker facility within the IxRS. Emergency procedures for revealing drug codes are given in [Section 9.5.4.5](#). If possible, before breaking the blind, the investigator should consult with the sponsor to ascertain the necessity of breaking the code.

At the conclusion of the study, all unused drug supplies are to be returned to the Eisai approved contract packaging vendor.

9.4.7 Prior and Concomitant Therapy

Medication (including over-the-counter medications) or therapy administered to the subject before the study (within 6 months of randomization) and during the study (starting at the date of informed consent) will be recorded on the Prior & Concomitant Medication eCRF or Non-Pharmacological Procedures eCRF. The investigator will record on the Adverse Event eCRF any AE for which the concomitant medication/therapy was administered. If the concomitant medication/therapy is being administered for a medical condition present at the time of entry into the study, the investigator will record the medical condition on the Medical History and Current Medical Condition eCRF.

Listings of prohibited and permitted drugs are provided in [Appendix 2](#). Prohibited medications are presented in [Listing 1](#) through [Listing 5](#). Medications that are permitted with restrictions are listed in [6](#) through [Listing 8](#). (revised per Amendment 04)

The following agents are not permitted before randomization (specific timeframes are shown below) and throughout the study until after the last treatment visit: (revised per Amendment 04)

- Drugs which may cause QTc prolongation are not permitted for a period of 5 half-lives or 14 days (whichever is longer) before randomization
- Strong CYP3A4 inhibitors are not permitted for a period of 5 half-lives or 14 days (whichever is longer) before randomization
- Live vaccines are not permitted within 3 months before randomization. This does not apply to non-live/inactivated vaccines
- Ig therapy and biologic drugs are not permitted within 6 months before randomization
- Systemic or ocular immunosuppressive or immunomodulatory drugs are not permitted for a period of 5 half-lives or 60 days (whichever is longer) before randomization. However, during the treatment period of the study, short term (not more than 14 days) use of steroids up to the equivalent of prednisolone 40 mg once daily is permitted after discussion with the Medical Monitor. Dosing with study drug should be suspended from the time steroid treatment is started. Complete blood count and lymphocyte subsets should be determined prior to starting steroid treatment and continue to be monitored weekly. Study drug may be resumed after discussion with the Medical Monitor when the following conditions are met: (1) treatment with steroids has been completed for at least 1 week; (2) total lymphocytes not <LLN; (3) no lymphocyte subsets are below the discontinuation threshold; (4) the investigator considers that the medical condition which required treatment with steroids has improved or resolved. Weekly testing of lymphocyte subset counts and CBC with differentials is required for 4 weeks following resumption of study drug administration. (revised per Amendment 04)

Subjects taking AChEIs or memantine must meet the following criteria in order to be included in the primary analyses:

- On a stable dose for 12 weeks before the Baseline cognitive assessments at Visit 2
- Remain on a stable dose while on study

Subjects who initiate treatment with an AChEI or memantine during the study, or who change their dose of AChEI or memantine while on study, will be allowed to continue in the study, but their clinical efficacy data will be censored from the time of drug initiation for any efficacy analyses. (revised per Amendment 05)

Subjects taking all other non-prohibited concomitant medications must meet the following requirements:

- Must be on stable dose for at least 4 weeks before randomization, except for medications that are administered as short courses of treatment or which are to be used intermittently as needed. Subjects who are on anticoagulants may have a variable dose but should have stable anticoagulation control for at least 4 weeks before randomization. They may be required to stop their anticoagulant medication prior to CSF collection and then restart this medication after the LP procedure, as per local guidelines. (revised per Amendment 04)
- Medications that are used as needed, rather than on a stable daily basis, and which are central nervous system (CNS) active and may affect cognitive function, are not permitted during a period of 72 hours before cognitive testing

Subjects who initiate treatment with or have dose adjustment of drugs not intended for treatment of cognitive impairment during the study may continue in the study if in the opinion of the investigator this will not interfere with study procedures or subject safety, and are not prohibited above. (revised per Amendment 05)

Antiplatelet therapy: (revised per Amendment 04)

- For subjects who consent to CSF sample collection: Either aspirin or clopidogrel (or any other antiplatelet drug which is not aspirin) are permitted in all subjects. Aspirin and clopidogrel (or any other antiplatelet drug which is not aspirin) in combination are also permitted but subjects who are on such a combination of antiplatelet drugs may be required to stop 1 or more of these antiplatelet drugs before the LP procedure and restart after the LP as per local guidelines.
- For subjects who do not consent to CSF sample collection: Aspirin and clopidogrel, individually or in combination, are permitted.

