9.7.1.1 Study Endpoints

9.7.1.1.1 PRIMARY ENDPOINT

- Safety and tolerability, which include incidence of TEAEs and SAEs, laboratory parameters, vital signs, and ECG parameters (revised per Amendment 05)

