9.7.1.2 Definitions of Analysis Sets

- The Randomized Set is the group of subjects who are randomized to study drug.
- The Safety Analysis Set is the group of subjects who receive at least 1 dose of study drug and have at least 1 postdose safety assessment.
- The Full Analysis Set (FAS) is the group of randomized subjects who receive at least 1 dose of study drug and have baseline and at least 1 postdose exploratory efficacy measurement. (revised per Amendment 05)
- The PK Analysis Set is the group of subjects with at least 1 quantifiable E2609 plasma concentration accompanied by a documented dosing history.
- The PD Analysis Set is the group of subjects who have a baseline PD measurement and at least 1 posttreatment PD measurement.

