9.7.1.6 Efficacy and Biomarker Analyses (revised per Amendment 05)

9.7.1.6.1 PRIMARY EFFICACY ANALYSIS

There is no primary efficacy endpoint. (revised per Amendment 05)

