9.7.1.2 Definitions of Analysis Sets

- The Randomized Set is the group of subjects who are randomized to study drug.
- The Safety Analysis Set is the group of subjects who receive at least 1 dose of study drug and have at least 1 postdose safety assessment.
- The Full Analysis Set (FAS) is the group of randomized subjects who receive at least 1 dose of study drug and have baseline and at least 1 postdose exploratory efficacy measurement. (revised per Amendment 05)
- The PK Analysis Set is the group of subjects with at least 1 quantifiable E2609 plasma concentration accompanied by a documented dosing history.
- The PD Analysis Set is the group of subjects who have a baseline PD measurement and at least 1 posttreatment PD measurement.

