9.7.1.8 Safety Analyses

Evaluations of safety will be performed on the Safety Analysis Set. The incidence of AEs (including changes from baseline in physical and neurological examinations, and dermatological assessments), out-of-normal-range laboratory safety test variables, abnormal ECG findings, out-of-range vital signs, suicidality (C-SSRS), and results of the sleep questionnaire, along with the change from baseline in laboratory safety test variables, ECGs, safety MRI, vital sign measurements, and cognitive decline assessment such as CBB will be summarized by treatment group using descriptive statistics. (revised per Amendment 05)

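### Section 9.4.7 and the synopsis make a stable AChEI/memantine dose on study a condition for the primary analyses; with safety now the only primary endpoint, this contradicts the Safety Analysis Set

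*Protocol*

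**What the plan says.** Section 9.4.7 of the Amendment 05 protocol, and the concomitant-therapy part of its synopsis in the same words, set a condition for users of cognitive enhancers: "Subjects taking AChEIs or memantine must meet the following criteria in order to be included in the primary analyses". Two criteria follow. The first is a stable dose for 12 weeks before the baseline cognitive assessments. The second is "Remain on a stable dose while on study".

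The next sentence, marked as revised by Amendment 05, covers subjects who start one of these drugs during the study and subjects who change their dose. Both may continue, but "their clinical efficacy data will be censored from the time of drug initiation for any efficacy analyses".

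Section 9.7.1.1.1 gives the primary endpoint as "Safety and tolerability, which include incidence of TEAEs and SAEs, laboratory parameters, vital signs, and ECG parameters". Section 9.7.1.6.1 adds: "There is no primary efficacy endpoint". Section 9.7.1.8 says: "Evaluations of safety will be performed on the Safety Analysis Set". Section 9.7.1.2 defines that set by at least one dose and at least one postdose safety assessment, and nothing else.

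**The concern.** Under the superseded design, with its primary efficacy objective, a stable-dose condition for the primary analysis had a recognizable purpose: a change in a cognitive enhancer confuses a cognitive outcome. Amendment 05 removed that objective and left safety as the only primary endpoint. The condition kept its reference to the primary analyses, so its literal target moved from efficacy to safety.

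That matters because staying on a stable dose is a post-randomization event. Leaving dosed subjects out of adverse event, laboratory and ECG summaries because of something that happened during treatment breaks the usual rule that everyone exposed is counted. The exclusion could also be tied to the outcome. Section 9.5.1.5.1 makes cognitive decline an adverse event when the investigator judges it excessive for the subject's recent history, and Section 9.7.1.8.6 treats cognitive decline as a safety assessment. It is plausible that worsening prompts a dose change, but this is an inference: the protocol covers any change and gives no reasons for it.

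The target is about 15 subjects per arm, so a few exclusions would be visible in the safety tables.

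**Working it through.** The protocol gives no figure on this point to reproduce, so the check is mainly textual.

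**Step 1: what primary can refer to.** Section 9.7.1.1.1 names safety and tolerability. Section 9.7.1.6.1 says there is no primary efficacy endpoint. Within this version, the primary analyses of Section 9.4.7 can literally mean only the safety analyses.

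**Step 2: who is counted.**

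| Source (Amendment 05 text) | Who enters the primary (safety) analysis |
|---|---|
| 9.4.7 and synopsis, inclusion condition | AChEI/memantine users only if the dose was stable before baseline and stays stable on study |
| 9.7.1.2 | Everyone with at least 1 dose and 1 postdose safety assessment |
| 9.7.1.8 | The Safety Analysis Set, with no further condition |
| 9.7.1.8.2 | The Safety Analysis Set for TEAEs; AEs also shown by prior AChEI/memantine treatment (no or yes) |
| 9.4.7, following sentence | Starters and dose-changers continue; only clinical efficacy data are censored, and only for efficacy analyses |

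The first row cannot be met together with the others for a user whose dose changes.

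**Step 3: likely origin.** The superseded synopsis included with the documents has a primary efficacy objective and a primary efficacy evaluation. The first stable-dose criterion is anchored to cognitive assessments. Both point to a leftover efficacy rule rather than a chosen safety exclusion.

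**Step 4: which version.** The contradiction lies wholly within the Amendment 05 text. The documents also hold part of a later text with Amendment 06 revisions. There the primary endpoint, the absence of a primary efficacy endpoint, the Safety Analysis Set and Section 9.7.1.8 are unchanged on this point. That text's Section 9.4.7 and synopsis are not shown.

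**Step 5: scale if the literal exclusion were applied.** The target of 60 over four equal arms gives 60/4 = 15 per arm; the ±20% range, 48 to 72, gives 12 to 18. The number excluded per arm is assumed, because the documents give neither the share of users nor the rate of dose changes. With n subjects left, the chance of at least one event at true rate p is 1 − (1 − p)^n. The one-sided 95% upper limit after zero events is 1 − 0.05^(1/n).

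| Excluded of 15 (assumed) | n | Chance of ≥1 event, p = 10% | Upper limit, 0 events |
|---|---|---|---|
| 0 | 15 | 0.794 | 18.1% |
| 1 | 14 | 0.771 | 19.3% |
| 3 | 12 | 0.718 | 22.1% |
| 5 | 10 | 0.651 | 25.9% |

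The effect on an observed rate depends on who is lost. Take 4 events in 15 (26.7%) and exclude 3 subjects. If all 3 had the event, the rate becomes 1/12 = 8.3%. If none did, it becomes 4/12 = 33.3%.

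**The case against.** The strongest reply is that the protocol already says how safety is analyzed. The sections that define the safety population contain no concomitant-medication condition, and a paragraph on prior and concomitant therapy would not normally override them. The sentence straight after the condition is more specific, was revised at Amendment 05, and limits the consequence to clinical efficacy data. This largely stands: it shows what was probably intended. It does not remove the conflict, because that sentence neither withdraws nor qualifies the inclusion condition above it, and the condition appears in two places.

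Three stronger readings are tempting, and the documents do not support them.

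- **That dose-changers will in fact be dropped from the safety results.** Sections 9.7.1.2 and 9.7.1.8 prescribe no such exclusion. What exists is a contradiction with a harmful literal reading.
- **That starters and dose-changers are treated unequally, with only the latter leaving the primary analysis.** The censoring sentence names both groups and gives them the same consequence.
- **That the safety comparison is biased towards no harm by a calculable amount.** The documents give no rate of use, of dose change, or of dose change after an adverse event. The example above shows a reported rate can move either way. A shift in one group's rate also does not establish a bias between arms.

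**Conclusion.** The concern holds as an internal contradiction in the Amendment 05 protocol. The inclusion condition in Section 9.4.7 and the synopsis, taken at its word, governs entry to the primary safety analysis through a post-randomization event, while the sections that define that analysis count every dosed subject with a postdose safety assessment. It is a wrongly stated rule, not a detail left to the SAP: an SAP author would inherit two incompatible statements of who is counted for the primary endpoint.

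The size cannot be derived from the documents. The illustrations rest entirely on an assumed number of exclusions, an assumed event rate and an assumed link to outcome. They show only that a few exclusions matter at about 15 per arm. Since the safety population itself is correctly defined, and the Amendment 05 sentence points to an efficacy-only intention, this is a correction worth making rather than evidence that the safety analysis is compromised. Confidence is limited to the Amendment 05 text; whether the wording persists under Amendment 06 cannot be checked here.

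**What to change.** In Section 9.4.7 and in the synopsis, replace the reference to inclusion in the primary analyses with wording that applies the stable-dose condition only to the exploratory clinical efficacy analyses. Add one sentence: all safety analyses use the full Safety Analysis Set, whether or not a subject starts or changes an AChEI or memantine on study. Before editing, check whether the current version (Amendment 06) still carries the wording, and make sure the SAP does not repeat the condition for safety.

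The cost is a sentence or two in two places. No data collection, visit, sample size or planned safety table changes.

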9.4.8 Treatment Compliance

Records of treatment compliance for each subject will be kept during the Treatment Period. CRAs will review treatment compliance during site visits and at the completion of the study.

9.4.9 Drug Supplies and Accountability

In compliance with local regulatory requirements, drug supplies will not be sent to the investigator (or if regionally required, the head of the medical institution or the designated pharmacist) until the following documentation has been received by the sponsor:

- A signed and dated confidentiality agreement

- A copy of the final protocol signature page, signed and dated by both the sponsor and investigator
- Written proof of approval of the protocol, the ICFs, and any other information provided to the subjects by the IRB/IEC for the institution where the study is to be conducted
- A copy of the IRB/IEC-approved ICF and any other documentation provided to the subjects to be used in this study
- The IRB/IEC membership list and statutes or Health and Human Services Assurance number
- A copy of the certification and a table of the normal laboratory ranges for the reference laboratory conducting the clinical laboratory tests required by this protocol
- An investigator-signed and dated FDA Form FDA 1572, where applicable
- Financial Disclosure form(s) for the principal investigator and all subinvestigators listed on Form FDA 1572, where applicable
- A signed and dated curriculum vitae of the principal investigator including a copy of the principal investigator's current medical license (required for United States sites) or medical registration number on the curriculum vitae
- A signed and dated Clinical Trial Agreement (CTA)
- A copy of the regulatory authority approval for the country in which the study is being conducted (if required), and the Import License (if required)

The investigator and the study staff (or if regionally required, the head of the medical institution or the designated pharmacist) will be responsible for the accountability of all study drugs (dispensing, inventory, and record keeping) following the sponsor's instructions and adherence to GCP guidelines as well as local or regional requirements.

Under no circumstances will the investigator allow the study drugs to be used other than as directed by this protocol. Study drugs will not be dispensed to any individual who is not enrolled in the study.

The site must maintain an accurate and timely record of the following: receipt of all study drugs, dispensing of study drugs to the subject, collection and reconciliation of unused study drugs that are either returned by the subjects or shipped to site but not dispensed to subjects, and return of reconciled study drugs to the sponsor or (where applicable) destruction of reconciled study drugs at the site. This includes, but may not be limited to: (a) documentation of receipt of study drugs, (b) study drugs dispensing/return reconciliation log, (c) study drugs accountability log, (d) all shipping service receipts, and (e) documentation of returns to the sponsor. All forms will be provided by the sponsor. Any comparable forms that the site wishes to use must be approved by the sponsor.

The study drugs and inventory records must be made available, upon request, for inspection by a designated representative of the sponsor or a representative of a health authority (eg, FDA, Medicines and Healthcare Regulatory Agency). As applicable, all unused study drugs and empty and partially empty containers from used study drugs are to be returned to the investigator (or if regionally required, the head of the medical institution or the

designated pharmacist) by the subject and, together with unused study drugs that were shipped to the site but not dispensed to subjects, are to be returned to the sponsor's designated central or local depot(s) during the study or at the conclusion of the study, unless provision is made by the sponsor for destruction of study drugs and containers at the site. Destruction at the site will only occur under circumstances where regulation or supply type prohibits the return of study drugs to the central or local depot(s). Approval for destruction to occur at the site must be provided by the sponsor in advance. Upon completion of drug accountability and reconciliation procedures by the site's personnel and documentation procedures by the sponsor's personnel, study drugs that are to be returned to the sponsor's designated central or local depot(s) must be boxed, sealed, and shipped back to the central or local depot(s) following all local regulatory requirements. In some regions, study drugs may be removed from the site and hand delivered to the central or local depot by sponsor representatives. Where study drugs are approved for destruction at the site, destruction will occur following the site's standard procedures and certificates of destruction will be provided to the sponsor.

Drug accountability will be reviewed during site visits and at the completion of the study.

9.5 Study Assessments

9.5.1 Assessments

9.5.1.1 Demography

Subject demography information will be collected at the Screening Visit. Demography information includes date of birth (or age), sex, race/ethnicity, native language, handedness, and highest education level.

